9.2 Sample Size and Accrual

For the primary endpoint of feasibility, we define a target rate of protocol completion (completion of radical cystectomy within sixteen weeks of initiation of PULSAR) of 90%, with a lower boundary of futility at 60%. A sample size of 24 patients provides 91% power to reject a 60% completion rate at a two-sided alpha of 0.05. Of note, this sample size was employed in the recent NABUCCO trial, which addressed a similar high-risk patient cohort³⁶. Allowing a 10% drop out rate increases the desired enrollment to a total of **27 patients**. Given the desired enrollment of 27 patients and the three-year trial period, this will require accrual of nine patients per year across all sites.

For the secondary endpoint of progression-free survival, the trial-eligible subset of our recently published historic series of cN+ bladder cancer patients achieved a 2-year recurrence-free survival rate of 30%¹⁵. A sample size of 24 patients provides 90% power to detect a 27% absolute increase in 2-year recurrence free survival with a one-sided alpha of 0.10 using the Kaplan-Meier log-rank test.

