Statistical Methodology	Proportion of patients completing the study will be calculated and the trial will be deemed successful if the number of patients completing the protocol exceeds the futility threshold of 60%. Progression-free survival, the secondary endpoint, will be estimated by the Kaplan-Meier method and compared with historic controls using the log-rank test.

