1.0 BACKGROUND AND RATIONALE

1.1 Disease Background

Muscle invasive bladder cancer (MIBC) has high metastatic potential and warrants aggressive treatment. Standard-of-care treatment in MIBC involves platinum-based neoadjuvant chemotherapy (NACT) followed by radical cystectomy (RC) with pelvic lymph node dissection (PLND) and urinary diversion¹⁻³. Bladder-conserving chemoradiation therapy is an appropriate alternative in select patients, though it is used in only a minority of cases in the United States⁴. Bladder cancer carries significant morbidity and mortality and has been cited as the most expensive malignancy to manage, on a per-patient basis, in the United States^{5,6}.

Metastatic spread to regional lymph nodes is an adverse prognostic factor in bladder cancer. In several large case series reported without use of neoadjuvant chemotherapy, patients with pathologically positive lymph nodes (pN+) at radical cystectomy had 5-year overall or disease-specific survival rates of only 22-30%⁷⁻¹⁰. The addition of neoadjuvant chemotherapy (NACT) or downstaging chemotherapy (DCT) in patients with clinically positive lymph nodes (cN+) improves outcomes, particularly in those who achieve a pathologic complete response to DCT^{11,12}. However, patients who fail to respond to downstaging or neoadjuvant chemotherapy have an especially poor prognosis, with a 5-year overall survival rate of only 16% in one recent series¹³. It should also be noted that a significant proportion (up to 25-50%) of patients with bladder cancer are ineligible for chemotherapy due to medical comorbidities¹⁴.

We recently reviewed the outcomes of patients undergoing radical cystectomy at UT Southwestern with bulky cN+ bladder cancer¹⁵. Among the subset of patients who did not receive or failed to respond to DCT, the 2-year progression-free survival was only 30%, despite aggressive salvage treatment. Importantly, a majority of patients (84%) in the study received downstaging chemotherapy and all were medically eligible for chemotherapy. This suggests that chemo-ineligible patients presenting with cN+ disease were not offered curative treatment. Direct comparisons with historic literature are difficult, due to widely varying definitions of cN+ disease; however, the progression-free survival of our bulky cN+ cohort closely parallels that of the cN2-3 and cM1a cohorts within one large published series¹¹, confirming that our bulky cN+ cohort represents an especially high-risk population.

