2.4 Secondary Endpoints

2.4.1 Progression free survival (PFS): Primary disease progression will be defined as any of the following. Progression-free survival will be measured from the date of the first PULSAR treatment.

1. Emergence of new sites of disease or locoregionally recurrent disease as defined by RECIST 1.1 criteria.

2. Pathologic demonstration of recurrent or metastatic disease (e.g. core needle biopsy, fine needle aspirate, diagnostic peritoneal biopsy).
3. Initiation of a patient on palliative or salvage treatment due to clinical concern for disease progression.
4. For patients with intraoperative concern for grossly incomplete disease resection (R2), the date of the first postoperative imaging study showing disease progression by RECIST 1.1 criteria (i.e., 20% increase in the sum of the diameters of all lesions, with an absolute increase of at least 5 mm; or the appearance of any new lesion).

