9.3 Data Analyses

The primary endpoint, protocol completion, will be assessed by calculating the proportion of patients completing radical cystectomy within sixteen weeks of initiating PULSAR treatment. If the proportion of patients undergoing cystectomy exceeds 60%, the null hypothesis (that use of ICI+PULSAR+RC is not feasible) will be deemed to have been rejected.

For the secondary endpoint, progression-free survival will be determined as described above, and will be reported by means of Kaplan-Meier survival curves, median progression-free survival time, and proportion of patients without progression at two years. Comparison will be made to the trial-eligible subset of patients in a historic control series using the log-rank test. The 2-year progression-free survival rate in the historic cohort was 30%. The null hypothesis will be rejected if the one-sided *p* value for the comparison is less than 0.10.

Additional planned analyses include the following, all of which will be reported with simple descriptive statistics (*n* / *N* and percentage):

Major complication rate: A major surgical complication will be defined as any postoperative complication of Clavien-Dindo Grade III or higher.

Pathologic outcomes: Pathologic outcomes will be defined as follows, based on the final surgical pathology report:

1. Pathologic complete response: no viable disease remaining in the specimen (ypT0 N0).
2. Pathologic non-muscle-invasive downstaging: primary tumor without muscle invasion, and no viable disease in lymph nodes (\leq ypT1 N0).
3. Pathologic organ-confined downstaging: primary tumor confined to detrusor muscle, and no viable disease in lymph nodes (\leq ypT2 N0).
4. Nodal complete response: no viable disease in lymph nodes, regardless of primary tumor stage (ypTany N0).

Residual disease: Residual disease at surgery will be defined as follows:

1. Microscopic residual disease (R1) will be defined as any positive soft tissue margin on the final surgical pathology report, excluding carcinoma *in situ* at ureteral margins.
2. Gross residual disease (R2) will be defined as any grossly positive tissue margin reported on a pathology report, *or* the operating surgeon's subjective report of grossly unresectable disease including bulky matted lymph nodes.

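### The 90% PFS power in 9.2 matches a one-sample calculation, but 9.3 plans a log-rank test against a historic subset of unstated size; 36 months also cannot hold two-year follow-up for the whole cohort

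*Combined protocol and SAP*

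**What the plan says.** For the secondary endpoint, 9.2 states: "A sample size of 24 patients provides 90% power to detect a 27% absolute increase in 2-year recurrence free survival with a one-sided alpha". That alpha is set at 0.10 and the test named is the log-rank. The reference is a 2-year rate of 30% in the trial-eligible part of the institution's own published series, so the target is 57%. (9.2 speaks of recurrence-free and progression-free survival interchangeably; I treat them as one endpoint.)

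The planned analysis in 9.3 reads: "Comparison will be made to the trial-eligible subset of patients in a historic control series using the log-rank test". The Study Summary agrees: PFS is to be "compared with historic controls using the log-rank test". The null hypothesis is rejected if the one-sided p value is below 0.10. Section 9.3 also reports the "proportion of patients without progression at two years".

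The historic series is described in 1.1, in percentages only: "a majority of patients (84%) in the study received downstaging chemotherapy", and "Among the subset of patients who did not receive or failed to respond to DCT, the 2-year progression-free survival was only 30" per cent. Neither the size of the subset nor its number of events or length of follow-up is given.

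On timing, the Study Summary gives a study duration of 36 months, and 9.2 says: "Given the desired enrollment of 27 patients and the three-year trial period, this will require accrual of nine patients per year across all sites". Section 2.4 says: "Progression-free survival will be measured from the date of the first PULSAR treatment". Sections 4.11, 5.2.5 and 5.4 provide two years of follow-up.

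**The concern.** A log-rank test between two groups of patients depends on the events in both. The historic group brings its own sampling error, and this does not shrink because the trial has 24 patients. A power figure for that test needs the historic numbers, and 9.2 uses none.

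PFS is secondary, but it is the only efficacy outcome in the plan with a hypothesis test and a rejection rule. If the historic subset is small, a non-significant result could be read as evidence against a 27-point gain, with 90% power behind it, when the test had much less. If the subset is large, the stated power is roughly right. A reader of the plan cannot tell which case applies.

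The timing matters for the same endpoint. If PFS were analysed when the stated 36 months end, most patients would not have two years of follow-up.

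**Working it through.** **Inputs.** From 9.2: 24 trial patients, 2-year rates of 30% and 57%, one-sided alpha 0.10 (z = 1.2816). From the Study Summary and 9.2: 36 months, 27 patients, nine per year. From 4.11: two years of follow-up from first PULSAR. Assumed, because the documents do not give them: the historic size m, exponential PFS, and 24 months of follow-up for everyone in both groups.

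**Step 1: reproduce the 90%.** Take 30% as a fixed value and use the exact binomial with n = 24.

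- At least 10 of 24 without progression: alpha 0.153, above 0.10.
- At least 11 of 24: alpha 0.074. Power is 88.6% at a true rate of 56% and 90.4% at 57%.

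So 57%, a gain of 27 points, is the first whole percentage point at which this rule reaches 90%. A one-sample log-rank test comes close. Expected trial events under the alternative are 24 × 0.43 = 10.32, against 22.10 predicted from the historic hazard over the same follow-up. Power by formula is Φ[(22.10 − 10.32)/√22.10 − 1.2816] = 89.0%; it is 87.8% on the log hazard ratio scale and 92.7% by simulation.

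**Step 2: the test that 9.3 plans.**

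- Hazard ratio: ln(0.57)/ln(0.30) = 0.467, so |ln HR| = 0.762.
- Expected events: d = 24 × 0.43 + m × 0.70.
- Trial share of patients: a = 24/(24 + m).
- Schoenfeld power: Φ[√(d·a(1−a)) × 0.762 − 1.2816].

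Example for m = 24: d = 27.1 and a(1−a) = 0.25, so √6.78 × 0.762 = 1.98, and Φ(0.70) = 76%.

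| Assumed historic patients | Expected events, both groups | Power, Schoenfeld | Power, simulated log-rank (40,000 runs) |
|---|---|---|---|
| 12 | 18.7 | 61% | 64% |
| 24 | 27.1 | 76% | 76% |
| 50 | 45.3 | 87% | 84% |
| 70 | 59.3 | 90% | 86% |
| 100 | 80.3 | 92% | 88% |
| 150 | 115.3 | 94% | 90% |
| 200 | 150.3 | 95% | 90% |

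Schoenfeld reaches 90% at about 71 historic patients (about 60 events: 10 trial, 50 historic). The simulation needs about 150-200; there the test is slightly conservative, with a null rejection rate of about 0.09. A third approximation, with variance 1/d1 + 1/d2 for the log hazard ratio (d1 and d2 being the events in each group), gives 74% at m = 24 and levels off near 88% however large m is.

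The absolute gain detectable with 90% power, against the stated 27 points, is 35 points at m = 24, 29-30 at 50, 27-29 at 70 and 26-28 at 100 (Schoenfeld and simulation).

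**Step 3: timing.** Accrual takes 27/9 = 3 years = 36 months. Adding 24 months of follow-up for the last patient gives about 60 months. Under uniform accrual, patients enrolled in the first 36 − 24 = 12 months reach 24 months of follow-up by month 36: 12/36, or about 9 of 27. Expected events among 24 trial patients would be about 7.2 at month 36, against 10.3 with full two-year follow-up. With an assumed m = 24 and the 1/d1 + 1/d2 variance, power would fall from 74% to 67%.

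**The case against.** The strongest reply is that the 90% is sound on its own terms. It follows from inputs in the plan once 30% is a fixed benchmark, and 9.3 repeats the 30% straight after naming the comparison. So the number is not uncheckable, and this part of the objection stands. What remains is that no section says the 30% is treated as fixed or that a one-sample test is meant, while 9.3 and the Study Summary both describe a comparison with historic controls.

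Second, any shortfall depends on a historic size that I had to assume, and the cited publication may give the counts. That also stands. A reader might infer that the PFS comparison is underpowered, or that the sponsor made a calculation error. The documents support neither: with a large subset the planned test has about the stated power by Schoenfeld or simulation, and the sponsor's method is not described.

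Third, 36 months may simply mean the accrual period. Read as total duration it could not hold the last patient's 16-week primary endpoint window or the 90 days after cystectomy either, so this reading is plausible, but no section says so. A reader might also infer that two-year follow-up is missing or impossible. It is not: 4.11, 5.2.5 and 5.4 provide it, and patients enrolled in about the first year could complete it within 36 months.

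Finally, PFS is secondary, and 9.3 also reports Kaplan-Meier curves, the median and the two-year proportion. This limits the weight of the point but does not remove it, because the test has its own rejection rule.

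**Conclusion.** The power statement and the planned test do not match. The stated 90% agrees with a one-sample calculation against a fixed 30% (90.4% by exact binomial). For the two-sample log-rank test in 9.3 it is unsupported unless the historic subset is large. Under exponential PFS and 24 months of follow-up in both groups, power is about 76% at 24 historic patients, 84-87% at 50, 86-90% at 70 and 88-92% at 100. The size at which it reaches 90% depends on the method, so no single threshold should be relied on. This is a claim without support, not one shown to be false.

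The stated duration conflicts with the plan's own accrual rate and follow-up: about 60 months are needed for two-year follow-up of everyone, against 36 stated, and only about a third of patients would have 24 months of follow-up at month 36.

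Both matters should be corrected. Neither affects the primary endpoint or the enrolment of 27.

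**What to change.** Make 9.2 and 9.3 agree, in one of two ways:

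- (a) In 9.3, and in the matching line of the Study Summary, specify a one-sample test against a fixed 30%, and state its exact alpha and power. For the exact binomial with at least 11 of 24 these are 0.074 and 90.4%, provided that the two-year status of all 24 is known. This needs no historic counts, but it treats the historic rate as known without error, which the text should say.
- (b) Keep the two-sample log-rank test, give the patients, PFS events and follow-up of the trial-eligible historic subset, and restate the power, or the gain detectable with 90% power, for that test.

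Then restate the study duration as about 60 months (36 of accrual plus 24 of follow-up), or label 36 months and the three-year period in 9.2 as accrual. State in 9.3 that PFS is analysed after the last patient's 24-month assessment.

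The cost is wording in the Study Summary, 9.2 and 9.3. The series is the institution's own, so the counts should be obtainable. No patients or visits are added, since two-year follow-up is already planned. The downside is that the stated PFS power may become less favourable and a longer duration is declared.

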9.3 Data Analyses

The primary endpoint, protocol completion, will be assessed by calculating the proportion of patients completing radical cystectomy within sixteen weeks of initiating PULSAR treatment. If the proportion of patients undergoing cystectomy exceeds 60%, the null hypothesis (that use of ICI+PULSAR+RC is not feasible) will be deemed to have been rejected.

For the secondary endpoint, progression-free survival will be determined as described above, and will be reported by means of Kaplan-Meier survival curves, median progression-free survival time, and proportion of patients without progression at two years. Comparison will be made to the trial-eligible subset of patients in a historic control series using the log-rank test. The 2-year progression-free survival rate in the historic cohort was 30%. The null hypothesis will be rejected if the one-sided *p* value for the comparison is less than 0.10.

Additional planned analyses include the following, all of which will be reported with simple descriptive statistics (*n* / *N* and percentage):

Major complication rate: A major surgical complication will be defined as any postoperative complication of Clavien-Dindo Grade III or higher.

Pathologic outcomes: Pathologic outcomes will be defined as follows, based on the final surgical pathology report:

1. Pathologic complete response: no viable disease remaining in the specimen (ypT0 N0).
2. Pathologic non-muscle-invasive downstaging: primary tumor without muscle invasion, and no viable disease in lymph nodes (\leq ypT1 N0).
3. Pathologic organ-confined downstaging: primary tumor confined to detrusor muscle, and no viable disease in lymph nodes (\leq ypT2 N0).
4. Nodal complete response: no viable disease in lymph nodes, regardless of primary tumor stage (ypTany N0).

Residual disease: Residual disease at surgery will be defined as follows:

1. Microscopic residual disease (R1) will be defined as any positive soft tissue margin on the final surgical pathology report, excluding carcinoma *in situ* at ureteral margins.
2. Gross residual disease (R2) will be defined as any grossly positive tissue margin reported on a pathology report, *or* the operating surgeon's subjective report of grossly unresectable disease including bulky matted lymph nodes.

Ureteroenteric stricture rate, defined as the need for procedural intervention performed for decompression of an obstructed kidney (e.g. percutaneous nephrostomy tube or surgical revision of ureteroenteric anastomosis), unless due to known or suspected disease recurrence.

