2.2 Secondary Objectives

2.2.1 To determine the 2-year progression-free survival (PFS) in patients with cN+ bladder cancer in all enrolled patients, and in the subset of patients completing the full protocol of ICI + PULSAR + RC.

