2.3 Primary Endpoints

2.3.1 The primary endpoint of the study is feasibility of RC after ICI + PULSAR, defined as the proportion of enrolled patients who complete three courses of PULSAR followed by radical cystectomy while remaining on ICI therapy, within sixteen weeks of initiation of PULSAR. It is anticipated that reasons for protocol non-completion may include progression to nonresectable disease and patient intolerance of treatment.

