9.0 STATISTICAL CONSIDERATIONS

9.1 Study Design/Study Endpoints

This is a single institution, single arm, phase II trial. We hypothesize that the combination of standard-of-care ICI with PULSAR will be feasible and does not result in delays in treatment. We define a target rate of protocol completion (completion of radical cystectomy within sixteen weeks of initiation of PULSAR) of 90%, with a lower boundary of futility at 60%.

The secondary endpoint is efficacy, defined by 2-year recurrence-free survival.

As discussed above, we additionally plan to assess safety (defined by the 90-day rate of Clavien-Dindo Grade \geq III complications following radical cystectomy); pathologic outcomes; rates of residual disease at surgery; and ureteroenteric anastomotic stricture rate.

If the incidence of Grade 3 or higher treatment-related adverse events convincingly exceeds 50%, a threshold we are comfortable with given the potential benefit of the regimen as well as our experience in managing the side effects in this patient population, we will temporarily halt the study and carefully review the available data at that point in order to suggest a potential modification. If we determine that high rates of adverse events are intrinsically related to protocol and no modification will reasonably decrease this rate to an acceptable threshold (below 50%), then we will terminate the study.

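### Section 9 scores the primary endpoint on timely cystectomy alone, whereas Section 2.3.1 also requires three PULSAR courses and continued ICI, so some 2.3.1 failures would count as successes

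*Combined protocol and SAP*

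**What the plan says.** Section 2.3.1 defines feasibility as "the proportion of enrolled patients who complete three courses of PULSAR followed by radical cystectomy while remaining on ICI therapy, within sixteen weeks" of the start of PULSAR. It names progression and intolerance of treatment as likely reasons for non-completion.

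Section 9 uses a narrower event:

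- Sections 9.1 and 9.2 both set a "target rate of protocol completion (completion of radical cystectomy within sixteen weeks of initiation of PULSAR) of 90"%, so the bracket itself says what completion means. Neither mentions the number of PULSAR courses or ICI.
- The first sentence of Section 9.3 says the endpoint "will be assessed by calculating the proportion of patients completing radical cystectomy within sixteen weeks of initiating PULSAR treatment".
- The decision sentence that follows begins "If the proportion of patients undergoing cystectomy exceeds 60%, the null hypothesis" and goes on to declare that null rejected. The null is that the combination of ICI, PULSAR and cystectomy is not feasible.

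The primary-endpoint text of Section 9 does not refer back to 2.3.1. The Study Summary speaks only of completing the protocol. On numbers, Section 9.2 sizes the trial at 24 and adds: "Allowing a 10% drop out rate increases the desired enrollment to a total of" 27. Section 4.13 replaces subjects removed before they have completed one fraction.

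**The concern.** The plan contains two definitions of its only success criterion, and the one attached to the calculation is the looser. Every patient who meets 2.3.1 also meets the Section 9.3 version, but not the reverse. The protocol allows the two to separate: Section 4.10 lets PULSAR stop early, for example for an unacceptable adverse event, and Section 4.13 does not replace a subject who has had one or two fractions. If such a patient then has a timely cystectomy, 2.3.1 records a failure and 9.3 a success. The same applies to a patient who stops ICI.

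The intolerance that 2.3.1 expects to cause failures could therefore disappear from the result. The rate calculated in 9.3 would not measure the three-part regimen named in its own null hypothesis. Two completion rates could be reported from the same data, with nothing in the plan to settle which is primary before the results are seen.

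**Working it through.** **Inputs.** From Section 9.2: null rate 0.60, target rate 0.90, n = 24, two-sided alpha 0.05, power 91%, drop-out 10%, enrolment 27. From Section 9.3: success if the proportion exceeds 60%. Assumed, because the documents give no figure: a further 5% or 10% of patients meet the 9.3 version but not 2.3.1.

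**1. The plan's own figure.** Exact binomial, n = 24, p = 0.60: P(X ≥ 19) = 0.0400 and P(X ≥ 20) = 0.0134. The smallest count with an upper tail of at most 0.025 is therefore 20. At p = 0.90, P(X ≥ 20) = 0.915, which reproduces the stated 91%. Enrolment: 24 / 0.9 = 26.7, rounded up to 27. Both figures are correct for 24 analysed patients.

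**2. One patient.** Under the written rule with 27 patients, 16/27 = 59.3% fails and 17/27 = 63.0% passes. One patient who meets only the 9.3 version reverses the conclusion. Each such patient adds 1/27 = 3.7 points.

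**3. Written rule (at least 17 of 27).** Because 2.3.1 completers are a subset of 9.3 completers, the chance of opposite conclusions is P(pass at p + gap) − P(pass at p).

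| True 2.3.1 rate | Gap 5% | Gap 10% |
|---|---|---|
| 60% | 0.670 − 0.458 = 0.21 | 0.843 − 0.458 = 0.39 |
| 80% | 0.999 − 0.989 = 0.01 | >0.999 − 0.989 = 0.01 |

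**4. Exact rule behind the 91% (at least 20 of 24).** At a true 2.3.1 rate of 60%, the chance of declaring feasibility is 1.3% when scored on 2.3.1. Scored on the 9.3 version it is P(X ≥ 20 | 0.65) = 4.2% or P(X ≥ 20 | 0.70) = 11.1%. Opposite conclusions:

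| True 2.3.1 rate | Gap 5% | Gap 10% |
|---|---|---|
| 60% | 0.042 − 0.013 = 0.029 | 0.111 − 0.013 = 0.098 |
| 80% | 0.713 − 0.460 = 0.25 | 0.915 − 0.460 = 0.46 |

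At a true rate of 90% with a 5% gap, the figure is about 8%.

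**5. What the 90% target refers to.** If 90% was set for timely cystectomy alone and 5% or 10% of patients fail only the PULSAR or ICI condition, the composite rate is 85% or 80%. Power on the composite with 24 patients is then 71.3% or 46.0%.

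**6. Counting enrolled patients.** If 10% drop out and 90% of the rest complete, the rate among the enrolled is 0.9 × 0.9 = 81%. For n = 27, P(X ≥ 21 | 0.60) = 0.042 and P(X ≥ 22 | 0.60) = 0.0155, so the exact two-sided 0.05 cut is 22. P(X ≥ 22 | 0.81) is about 59%. If 90% holds among all 27 enrolled, it is 95.3%.

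**The case against.** The best defence is that Section 9 uses protocol completion as shorthand for 2.3.1. The null in 9.3 names all three parts of the regimen, and the Study Summary speaks of completing the protocol. That makes the intention plausible, but 9.1 and 9.2 spell out the narrower event in brackets and 9.3 gives it as the calculation. An analyst who follows 9.3 would not check fractions or ICI.

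A reader might infer more than the documents support:

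- **That 9.3 counts surgery after week 16 as success.** The decision sentence omits the window, and 9.1 hypothesises that treatment "the combination of standard-of-care ICI with PULSAR will be feasible and does not result in delays in treatment". But the sentence just before it states the window, and the decision sentence most naturally refers back to that proportion. This is probably loose drafting.
- **That the scoring of held PULSAR, an ICI switch or a low ICI dose count is undefined.** A patient without three courses plainly fails 2.3.1. Section 4.8 permits switching, and a switched patient is still on ICI. The two-dose minimum in 4.8 is a recommendation, not part of the endpoint.
- **That the plan excludes drop-outs from the denominator.** No section says so. The word patients in 9.3 is compatible with enrolled patients in 2.3.1. Section 4.13 governs recruitment, and the 10% in 9.2 is a planning allowance. What is missing is narrower: how to count a subject who never starts PULSAR and so has no 16-week clock.
- **That the PFS subset inherits the problem.** Section 2.2.1 describes its subset as "in the subset of patients completing the full protocol of ICI + PULSAR + RC" and so names its own components.

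It is also fair to object that the 5% and 10% gaps have no source in the documents.

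**Conclusion.** The contradiction is real, and following 9.3 literally would count 2.3.1 failures as successes. The direction is certain: the reported completion rate can only be equal or higher. The size is not known and rests on the assumed gaps.

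Where the conclusion is most exposed depends on the decision rule. Under the written above-60% rule the risk lies near the threshold and is about 1% at a true rate of 80%. It would be wrong to conclude from this that the discrepancy is harmless well above 60%: under the exact rule behind the 91% power, disagreement at 80% is 25% or 46%. The gap between the two rules is a separate matter.

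The 91% power and the enrolment of 27 are not in error. Because this is the sole success criterion and the correction is to the text, it should be made before the primary analysis.

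**What to change.** 1. Use the full 2.3.1 definition, including the 16-week window and the denominator of enrolled patients, in 9.1, 9.2, both primary-endpoint sentences of 9.3 and the Study Summary. Report cystectomy within 16 weeks as a descriptive rate.
2. State in 9.3 that patients who drop out after starting PULSAR count as non-completers. State how subjects who never start PULSAR, including those replaced under 4.13, are counted. Give the set that started PULSAR as a sensitivity analysis.
3. State in 9.2 that the 91% power is for 24 analysed patients with a 90% rate on the 2.3.1 composite. Disclose there that a 10% drop-out counted as failure could bring the enrolled rate to 81% and exact power at 27 to about 59%.

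The cost is wording only. No patients or visits are added, and the 60% threshold stays. The reported rate may be less favourable, by as much as nine points in the drop-out illustration (90% to 81%).
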